16.10. Suspension or Early Termination

The Sponsor reserves the right to discontinue the study at any stage, with written notice to all investigators and reviewing IRB. Similarly, investigators may withdraw from the study at any time, subject to providing written notification to the Sponsor 30 days prior to the date they intend to withdraw.

The Sponsor and investigators will be bound by their obligation to complete the follow-up of subjects already participating in the study. If the study is terminated or suspended, no additional enrollment will be allowed unless otherwise informed by the sponsor. The current subjects will be followed according to the protocol, and information obtained during subject follow-up shall be reported to the Sponsor on the appropriate eCRF.

If the study is terminated prematurely or suspended by the sponsor, the sponsor will promptly inform the investigators and regulatory authorities (if required) of the termination and the reason(s). The IRB will also be promptly informed and provided with the reason(s) for termination or suspension by the sponsor or by the Investigator. The Investigator will promptly inform the subjects and assure appropriate therapy and follow-up for the subject, as needed.

If the Investigator (or IRB) terminates or suspends the investigation without the prior agreement of the sponsor, the Investigator will promptly inform the sponsor, the institution (if required), and the IRB and provide a detailed written explanation of the termination or suspension. The sponsor will inform the regulatory authorities (if required.)

In the case of early termination of the study, all study subjects should be followed until the resolution of any pending adverse event(s.)

Medtronic reserves the right to discontinue the study at any time for administrative or other reasons. Written notice of study termination will be submitted to the Investigator in advance of such termination. Possible reasons for considering study suspension or termination of the study for all centers include but are not limited to:

Medtronic Business Restricted

- Failure to obtain initial IRB approval or annual renewal of the study;
- Consistent non-compliance to the CIP (e.g., failure to adhere to inclusion/exclusion criteria, failure to follow subjects per scheduled follow-ups, failure to implement required corrective and preventive actions, etc.);
- Lack of enrollment;

Appendix A – Pediatric Anesthesia Emergence Delirium (PAED) [1]

The PAED Scale	
Item scores are added together for a total score, with higher scores indicating more severe delirium	
Items 1,2,3 are scored as follow: 4 = not at all 3 = just a little 2 = quite a bit 1 = very much 0 = extremely	Items 4 and 5 are scored as followed 0 = not at all 1 = just a little 2= quite a bit 3 = very much 4 = extremely
Items	Sore
1. Child makes eye contact with caregiver	
2. Child's actions are purposeful	
3. Child is aware of his/her surroundings	
4. Child is restless	
5. Child is inconsolable	
Total Score	

Appendix B – Wong-Baker FACES Scale [2, 3]

Wong-Baker FACES® Pain Rating Scale

©1983 Wong-Baker FACES Foundation. www.WongBakerFACES.org
Used with permission. Originally published in *Whaley & Wong's Nursing Care of Infants and Children*. ©Elsevier Inc.

Date of Assessment: _____ Time of Assessment: _____

Appendix C – Modified Aldrete Scoring System [15, 16]

ACTIVITY	Able to move all extremities voluntarily on command	2
	Able to move 2 extremities voluntarily on command, some weakness	1
	Unable to move extremities	0
RESPIRATION	Able to deep breathe and cough without assistance	2
	Requires airway assistance	1
	Apnea	0
CIRCULATION	Blood pressure and heart rate are within 20% of presedation level	2
	Blood pressure and heart rate are within 20-50% of presedation level	1
	Blood pressure and heart rate are less than 50% of presedation level	0
CONSCIOUSNESS	Fully awake, able to answer questions as appropriate	2
	Arousable with verbal stimulation	1
	Unresponsive	0
OXYGENATION	Able to maintain oxygen saturation >92 percent on room air	2
	Requires supplemental oxygen to maintain oxygen saturation >92 percent	1
	Oxygen saturation <92 percent even with supplemental oxygen	0

19. Version History

Version	Summary of changes	Author(s)/Title
1.0	
Not Applicable, New Document	[name]./ Sr. Clinical Program Manager [name]/Sr. Clinical Research Specialist
2.0	
Revision to new Operating UnitCorrection to Wong-Baker Collection criteria	[name], Sr. Clinical Research Specialist
3.0	
Changes to title page to remove unused rowsAddition of signal quality index (SQI) to glossaryChange definition of time of surgical procedure to maintenance duration to align with statistical analysis planIncrease number of sites up to eightAddition of pre-operative vitals obtained in pre-operative holding to baseline/enrollment visit procedures and assessmentsChange of surgeries approved for study to allow for approval of additional surgery types by study teamChange in allowed % of time outside of BIS range for BIS-guided subjects from 25% of 35% to improve number of qualifying cases (business decision)Change in Wong-Baker FACES Pain Rating Scale to be performed only when subject is awake to avoid unnecessary protocol deviationsCompletion of recovery assessments changes from every 5 minutes to every 15 minutesAddition of required variables to list of timepoints for BIS, ETSevo, FiO2, and EtO2 data collection needed for outcome analysisClarification of procedure and recovery variables	[name]., Sr. Clinical Research Specialist

	
12. Update of missing references throughout document13. Update to data collection table 5 to include emergence and adverse event assessment in PACU if applicable14. Removal of confusing language in 10.7 Baseline around what is recorded where. All data should be recorded in source and CRF per section 16.2 and Case Report Form Completion Guidelines.15. Clarity around Adverse Event language16. Update to Clinical Affairs Clinical Study Manager (CSM) contact from [name] to [name] as [name] is no longer the CSM or Safety Manager17. Minor grammar/spelling revisions18. Update to 056-F275, v D Clinical Investigational Plan Template	
4.0	
1. Sample size section in summary and 14.2 updated to reflect the required number of cases to be analyzed.2. Minor grammar/spelling revisions	[name]., Sr. Clinical Research Specialist
4.1	
1. Update to current template	[name]., Sr. Clinical Research Specialist

SAS	Statistical analysis system
SP	Standard practice

3. Introduction

This statistical analysis plan (SAP) specifies the statistical methods to be implemented for the analysis of data used in the Medtronic clinical study titled as “Bispectral Index and End-Tidal Anesthetic Gas Concentration in Pediatric Patients undergoing Sevoflurane Anesthesia (BTIGER)”. It elaborates the statistical analyses specified in the BIS BTIGER CIP 2.0, dated 22-FEB-2021.

This document is created for internal use as a guideline for study Biostatistician and Statistical Programmer(s). Analysis results obtained from the analyses outlined in this document will be the basis of the Clinical Study Report (CSR) for this study.

As with any statistical analysis plan, the proposed methods and approaches to the data analysis should be considered as flexible to accommodate necessary changes. Changes to the plan may arise if the emerging picture suggests that deviations from the original plan would provide a more reliable and valid analysis of the data. The purpose of this plan is to provide general, and in some instances, specific guidelines from which the analysis will proceed. Nonetheless, sound statistical reasoning must substantiate deviations from these guidelines.

The planned analyses identified in this statistical analysis plan (SAP) may be included in regulatory submissions and/or future manuscripts. Additional exploratory analyses, not identified in this SAP, may be performed to support the clinical development program. Any post-hoc, or unplanned, analyses that are performed but not identified in this SAP will be clearly identified in the CSR.

General anesthesia (GA) is a reversible state of controlled unconsciousness that is achieved with drugs that prevent awareness, pain, recall, distress, and movement in patients during surgery. Maintaining an adequate level of anesthesia depth is essential to the attenuation of these responses. During the surgery operation, monitoring the depth of anesthesia could help the anesthesia professional avoid intraoperative awareness and help to ensure that an appropriate dose of anesthetic drugs is given for each patient.

Bispectral Index (BIS™) technology monitoring uses the processed electroencephalogram (EEG) signals to measure sedation depth based on level of consciousness (LOC) signals. Its values quantify changes in the electrophysiologic state of the brain during anesthesia. It has been known that the use of BIS™ during general anesthesia improves the titration of anesthetics in adults.

4. Study Objectives

1.1 Primary Objective

To characterize BIS™ performance with the anesthetic agent in pediatric patients 4 to 18 years of age.

1.2 Endpoints

The primary endpoints are End-Tidal Sevoflurane concentration in both patient groups acquired during maintenance of anesthesia.

The secondary and exploratory endpoints include:

- Recovery assessments in patients receiving BIS™ monitoring compared to standard anesthetic practice:
 - Emergence,
 - PACU discharge readiness using Modified Aldrete Score
 - Anesthesia Airway Management (AAM)
- Clinical Anesthesia Assessment, recorded as the incidence of movements, grimacing, eye opening, tearing, sweating, mydriasis and cardiovascular changes while undergoing anesthesia
- Pediatric Anesthesia Emergence Delirium (PAED),
- Wong-Baker FACES Pain Rating Score

5. Investigation Plan

This is a multi-center, prospective, randomized controlled study to collect data to compare the performance of standard practice (SP) group with the BIS™ monitoring (BIS) group. Pediatric patients between the ages of 4 to 18 years undergoing routine sevoflurane general anesthesia with an expected surgical procedure duration of 30 minutes or more will be recruited. General surgeries include abdominal, urological, orthopedic, or ophthalmological procedures with an American Society of Anesthesiologists physical status of I - III. Children will be recruited from the preoperative clinic and will be divided into three age groups:

- 4 to 8 years
- 9 to 12 years
- 13 to 18 years

A control group, comprising of the first 2–4 subjects at each site will be enrolled to train the site team on the new technology and to determine the quality of data collection before randomization. Afterward, randomization will proceed based on the Sponsor's assessment of data quality.

For the BIS group, sevoflurane will be adjusted to achieve a target BIS™ values of 45–60 during maintenance of anesthesia and BIS™ values of 60–75 beginning of skin closure. For the SP group, sevoflurane administration will be at the discretion of the anesthesiologist using clinical signs and hemodynamic changes to adjust anesthetic concentration.

6. Determination of Sample Size

The first 2 - 4 subjects at each site will be enrolled to train the site team on the new technology and to determine the quality of data collection prior to randomization ($n = 16-32$). They will not be randomized and will not be included in the final analysis. For the analysis, a minimum of 36 subjects are required in each age group (18 per treatment group) for a minimum of 108 qualifying data sets. Subjects with non-qualifying data sets will be rejected and replaced with a newly randomized subject. This sample size was independently powered for each of the 3 age groups based on data from a previously published study conducted by Emory University.

7. Statistical Methods

7.1 Study Subjects

7.1.1 Disposition of Subjects

Subject disposition will be summarized with frequency tables.

7.1.2 Clinical Investigation Plan (CIP) Deviations

Discuss potential CIP deviations or violations and how they will be reported.

7.1.3 Analysis Sets

All study subjects (excluding training) that satisfied the inclusion and exclusion criteria will be included in the analysis.

7.2 General Methodology

All statistical analyses will be performed using Statistical Analysis System (SAS) for Windows (version 9.4 or higher, SAS Institute Inc. Cary, NC) or other widely accepted statistical or graphical software. In general, data for all study subjects will be presented. Individual data will be presented in subject listings.

Descriptive statistics will be used to present the data and to summarize study outcomes. Discrete variables will be presented using frequency distributions and cross tabulations. Continuous variables will be summarized by presenting the number of observations (n), mean, standard deviation, median, minimum, and maximum values.

7.3 Center Pooling

The clinical study will be conducted under a common protocol for each investigational site with the intention of pooling the data for analysis. Every effort will be made to promote consistency in study execution at each study site.

An assessment of data poolability of the sites will be performed using a mixed-effect model for the primary endpoint. A significance level of 0.15 will be considered. Sites with fewer than five subjects will be combined into large sites to ensure statistical robustness.

If the sites are found to be significantly heterogeneous with respect to the primary endpoint, additional analyses will be conducted to further assess differences between sites in baseline and procedural variables that might contribute the differences.

7.4 Handling of Missing, Unused, and Spurious Data and Dropouts

The primary analysis will include all evaluable data and missing values will not be imputed. BIS™ values that are outside of the specified range of 45 – 60 during maintenance of anesthesia for >25% of the maintenance period will be considered a protocol deviation and will result in an exclusion of the subject from the primary analysis. The excluded subject will be replaced, and data from all excluded subjects will be noted and discussed in the final study report. Additionally, sensitivity analysis (e.g., multiple imputation) may be performed as appropriate to assess the robustness of study results.

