For the BIS™ group, sevoflurane will be titrated to achieve a target BIS™ value of 45 – 60 during maintenance of anesthesia and a target BIS™ value of 60 – 75 beginning at the start of skin closure. In order to protect against inadequate or excessive anesthesia in the BIS™ guided group, the subject will be assessed approximately every 5 minutes for signs of anesthesia. In the event of hypertension and/or tachycardia (>20% above baseline) unexplained by surgical manipulation and or signs of autonomic or somatic responses (e.g., diaphoresis, movement) an additional dose of opioid will be administered. If that does not resolve the situation, then the anesthesiologist may alter the anesthetic concentration outside the BIS™ guidelines to assure adequate anesthesia. In the event of hypotension and/or bradycardia (>20% below baseline), fluids and/or vasopressor will be administered. If that does not resolve the situation, then the anesthesiologist may alter the anesthetic concentration outside the BIS™ guidelines. Subjects with BIS™ values that are outside of the specified range of 45 – 60 during maintenance of anesthesia for >35% of the maintenance duration will be considered a protocol deviation and the subject will be excluded from the final data analysis. The subject will be replaced by an additional enrolled subject. The excluded subject will continue to be monitored for any safety events and the clinician will ensure medical care is provided for any safety event that occurs. Data from excluded subjects will be acknowledged in the final study report but will not be included in the primary statistical analysis. The exception to this exclusion is any data that is outside of the specified range of 45 – 60 as a result of the anesthesiologist titrating sevoflurane as a result of clinical signs or cardiovascular changes defined above. The end-tidal sevoflurane concentration will be continuously recorded. Fentanyl or morphine will be administered at the discretion of the anesthesiologist, for example, 1.5 mcg/kg at induction and 0.75 mcg/kg every 30 minutes in accordance with usual clinical indications.

For the SP group, sevoflurane, fentanyl, propofol, and morphine will be administered at the discretion of the anesthesiologist for example, fentanyl and morphine at 1.5 mcg/kg at induction and 0.75 mcg/kg every 30 minutes in accordance with usual clinical indications.

Medtronic Business Restricted

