In the BIS™ group, fentanyl and morphine administration will be at the discretion of the anesthesiologist, for example, fentanyl and morphine 1.5 mcg/kg at induction and 0.75 mcg/kg every 30 minutes, using clinical signs and cardiovascular changes, however sevoflurane will be adjusted to achieve a target BIS™ values of 45 – 60 during maintenance of anesthesia and BIS™ values of 60 – 75 beginning of skin closure. Subjects with BIS™ values that are outside of the specified range of 45 – 60 during maintenance of anesthesia for >35% of the maintenance duration will be considered a protocol deviation and the subject will be excluded from the final data analysis and will be replaced by an additional subject. The excluded subject will continue to be monitored for any safety events and the clinical will ensure that medical care is provided should a safety event occur. Data from the excluded subject will be acknowledged in the final study report but will not be included in the primary statistical analysis. The exception to this exclusion is any data that is outside of the specified range of 45 – 60 as a result of the anesthesiologist titrating medications as a result of clinical signs or cardiovascular changes defined above. Additionally, data points will be excluded if significant artifact is present or if the sevoflurane concentration or BIS™ value is missing.

At the completion of the surgery, and after confirmation of the return of neuromuscular function, sevoflurane will be discontinued, and discontinuation time will be recorded, and as applicable, extubation will be performed when the patients demonstrate the purposeful movement, facial grimace, or eye-opening to jaw thrust.

Event Markers and Assessments

During the case, the time of events (for example start of induction, LOC, airway management /intubation (as applicable), the start of the procedure, incision, N₂O off (as applicable), sevoflurane off, extubation (as applicable), eye-opening, end of the procedure, move to PACU, and PACU discharge readiness) will be recorded.

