10.9.3.3 BIS™ Guided Group

In the BIS™ group, sevoflurane will be adjusted to achieve a target BIS™ values of 45 – 60 during maintenance of anesthesia and BIS™ values of 60 – 75 beginning of skin closure. Subjects with BIS™ values that are outside of the specified range of 45 – 60 during maintenance of anesthesia for >35% of the maintenance duration will be considered a protocol deviation and the subject will be excluded from the final data analysis and will be replaced by an additional subject. The excluded subject will continue to be monitored for any safety events and the clinical will ensure that medical care is provided should a safety event occur. Data from the excluded subject will be acknowledged in the final study report but will not be

included in the primary statistical analysis. The exception to this exclusion is any data that is outside of the specified range of 45 – 60 as a result of the anesthesiologist titrating medications as a result of clinical signs or cardiovascular changes defined above. Additionally, data points will be excluded if significant artifact is present or if the sevoflurane concentration or BIS™ value is missing.

At the completion of the surgery, and after confirmation of the return of neuromuscular function, sevoflurane will be discontinued, and discontinuation time will be recorded, and as applicable, extubation will be performed when the patients demonstrate the purposeful movement, facial grimace, or eye-opening to jaw thrust.

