If the sites are found to be significantly heterogeneous with respect to the primary endpoint, additional analyses will be conducted to further assess differences between sites in baseline and procedural variables that might contribute the differences.

Medtronic Business Restricted

Missing Data

The primary analysis will include all evaluable data and missing values will not be imputed. BIS™ values that are outside of the specified range of 45 – 60 during maintenance of anesthesia for >35% of the maintenance duration will be considered a protocol deviation and will result in an exclusion of the subject from the primary analysis. The excluded subject will be replaced, and data from all excluded subjects will be noted and discussed in the final study report. Additionally, sensitivity analysis (e.g., multiple imputation) may be performed as appropriate to assess the robustness of study results.

Additional Summaries and Considerations

Cardiovascular variables will be summarized for both treatment groups. The incidence of hypotension will be summarized and compared to anesthesia sedation levels.

The anesthetic requirements with the BIS™ value, the percentage of time during maintenance with BIS™ value within the specified ranges, and number of episodes and duration of burst suppression will be assessed for the BIS and SP groups.

Additional endpoints, including the PAED scale, PACU discharge readiness and a subgroup analysis for subjects requiring neuromuscular blockade, will be evaluated by using descriptive statistics and compared between both groups.

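### BIS-group subjects are excluded and replaced after randomisation for time outside BIS 45–60; the cut-off is 35% in the protocol and 25% in the SAP, and no comparison of all randomised subjects is clearly specified

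*SAP*

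**What the plan says.** The primary endpoint is end-tidal sevoflurane during maintenance, compared between the BIS and SP arms by a t-test or Wilcoxon test (Protocol 14.1, SAP 7.9). Allocation is 1:1 within age group and site. The rule on time outside BIS 45–60 appears in these places:

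- **Protocol 10.9.3.3 (BIS Guided Group):** "for >35% of the maintenance duration will be considered a protocol deviation and the subject will be excluded from the final data analysis". The subject is replaced. The Synopsis has the same rule in its BIS-group text under Study Design and under Maintenance anesthesia. Study Design adds: "Data from excluded subjects will be acknowledged in the final study report but will not be included in the primary statistical analysis".
- **Protocol 14.1 (Missing Data):** "for >35% of the maintenance duration will be considered a protocol deviation and will result in an exclusion of the subject", this time from the primary analysis. No arm is named and no exception is given.
- **SAP 7.4:** "for >25% of the maintenance period will be considered a protocol deviation and will result in an exclusion of the subject", again from the primary analysis, with no arm and no exception.
- **Exception:** out-of-range data are exempt when they come from "titrating sevoflurane as a result of clinical signs or cardiovascular changes defined above" (Synopsis, Study Design) or from "titrating medications as a result of clinical signs or cardiovascular changes defined above" (Synopsis, Maintenance anesthesia, and 10.9.3.3).
- **Further analysis:** Protocol 14.1 and SAP 7.4 both say only that "sensitivity analysis (e.g., multiple imputation) may be performed as appropriate to assess the robustness of study results".
- **Analysis set:** SAP 7.1.3 takes in every non-training subject who met the eligibility criteria. Protocol 10.14.1 says that all data up to a subject's exit will be used.

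The SAP states that it elaborates CIP 2.0, whereas the protocol's version history runs to 4.1.

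**The concern.** Time in range is known only after the anesthetic has been given. In the procedural text the rule removes guided subjects for whom titration did not hold the target, and it leaves the SP arm whole. The retained BIS arm is then a selected group set against an unselected one. The selecting variable is not incidental: SAP 7.9 plans to fit BIS against sevoflurane concentration, and sevoflurane is the endpoint. Replacement restores the count but not the comparability that randomisation gave.

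The inconsistencies add a second problem. Two statisticians who each follow one document would analyse different subjects, and nothing fixes the choice before the data are seen. An optional sensitivity analysis does not close the gap. The one example given, multiple imputation, addresses missing values, whereas the sevoflurane values of excluded subjects would normally have been observed.

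**Working it through.** **1. The plan's own figure.** Protocol 14.2 gives a difference of 0.5%, SD 0.5%, 18 per arm in each age group and two-sided 0.05. By the normal approximation, power = Φ(0.5/(0.5·√(2/18)) − 1.96) = Φ(3.00 − 1.96) = 0.851. The noncentral t gives 0.830. The claim of more than 80% reproduces, but for 18 qualifying subjects per arm after exclusion and replacement.

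**2. The texts side by side.**

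| Item | Synopsis and Protocol 10.9.3.3 | Protocol 14.1 | SAP 7.4 |
|---|---|---|---|
| Cut-off | >35% | >35% | >25% |
| Arm | BIS group | not named | not named |
| Exception | sevoflurane titration, or titration of medications | none | none |
| Excluded from | both the final and the primary analysis are named | primary analysis | primary analysis |

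The two terms in the first column leave the standing of these subjects in the secondary analyses open. SAP 7.1.3 and Protocol 10.14.1, read literally, would keep subjects whom SAP 7.4 removes.

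**3. How bias would arise (illustration).** The endpoint SD of 0.5% is from Protocol 14.2. Everything else is assumed, with no source in the documents: no true effect, subject-mean BIS normal with mean 50 and SD s of 4 or 7, within-subject SD 5, and between-subject correlation r of −0.2 to −0.5. The 35% rule is applied to the BIS arm only, the exception is ignored, and subjects are replaced until 18 are kept.

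A subject with mean BIS m is out of range for a fraction p(m) = Φ((45 − m)/5) + 1 − Φ((60 − m)/5). Setting p = 0.35 gives m = 46.99 and 58.01, so subjects with means between these values are kept. With a = (46.99 − 50)/s and b = (58.01 − 50)/s, the mean standardised BIS of those kept is z = (φ(a) − φ(b))/(Φ(b) − Φ(a)), and bias = r × 0.5 × z.

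| s | Excluded | z | Bias, r = −0.2 | Bias, r = −0.5 | Type I error at 18/arm, r = −0.2 / −0.5 (simulated) |
|---|---|---|---|---|---|
| 4 | 25% | 0.328 | −0.033% | −0.082% | about 5% / 8% |
| 7 | 46% | 0.290 | −0.029% | −0.072% | about 5% / 7% |

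At r = −0.03, the only correlation between BIS and sevoflurane quoted as a figure (Protocol 4.1.3.1), bias is −0.03 × 0.5 × 0.328 = −0.005% and type I error is about 5%. If guided-arm BIS is centred at 52.5, z = 0 and there is no bias at any r. A mean of 55 instead of 50, or a positive r, reverses the sign.

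**4. The cut-off conflict under the same assumptions.** Setting p = 0.25 narrows the retained means to 48.55–56.45. Total exclusion rises from 25% to 41% (s = 4) or from 46% to 60% (s = 7). Of those kept at 35%, the SAP's limit would drop a further 22% or 25%, roughly 4 of 18.

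**5. Power if everyone is kept.** At 18 per arm and SD 0.5%, power by the noncentral t is 83% for a difference of 0.5%, 64% for 0.4% and 42% for 0.3%. If 20% or 40% of guided subjects gained none of the 0.5% difference (assumed), the overall difference would be 0.5 × 0.8 = 0.4% or 0.5 × 0.6 = 0.3%, and 80% power would need about 25 or 44 per arm (normal approximation).

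**The case against.** **The numbers are soft.** This stands. Within-subject SD, between-subject SD and r are all unsourced. The sigmoid model in SAP 7.9 is a concentration–response curve and does not supply the between-subject correlation under titration. At the one quoted r the bias all but vanishes. The exclusion rates are also fragile: at within-subject SD 8, even a perfectly centred subject is out of range 2Φ(−7.5/8) = 35% of the time. A reader might infer that the rule tilts the trial towards BIS, or badly inflates type I error; the documents support neither.

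**The arm is not really in conflict.** This also stands. Protocol 14.1 and SAP 7.4 are silent rather than contradictory. The range 45–60 is a target only for the BIS group, SP clinicians are blinded to BIS, and the version history (section 19) speaks of a limit "outside of BIS range for BIS-guided subjects from 25% of 35% to improve number of qualifying cases (business decision". A reader might infer that SP subjects are to be filtered too, which would remove many of them. That reading is strained, and naming the arm settles it.

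**Exclusions may be defined elsewhere.** Protocol 14 refers data exclusion to a Data Management Plan that is not among the documents. That weakens any complaint that SAP 7.1.3 omits the exclusions for short maintenance, intraoperative regional anesthesia and dexmedetomidine, which apply to both arms. It does not resolve two different cut-offs in current text, nor supply an analysis of all randomised subjects.

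**The SAP may simply be out of date.** Probably so on the cut-off. Yet its sample-size section matches current Protocol 14.2 almost word for word, so a reader cannot tell which parts were meant to be current.

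**Conclusion.** The concern holds as a defect of the analysis set, and it can be read from the text without simulation. The primary comparison applies a post-randomisation filter to the BIS arm, on a variable tied to the endpoint. The current documents disagree on its cut-off (35% or 25%), its exception and its scope. SAP 7.1.3 and SAP 7.4 disagree on who is analysed.

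It would go too far to say that the plan rules out an as-randomised analysis, because SAP 7.1.3 could be read as a basis for one. What can be said is that none is clearly specified or required.

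The bias has no size or direction that the documents can fix. The illustrated range, from zero to about 0.08% sevoflurane against a design difference of 0.5%, rests wholly on the inputs assumed above and is not a bound. The case for change is that randomisation should protect the primary test whatever those inputs turn out to be.

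**What to change.** 1. In SAP 7.1.3 and 7.4 and Protocol 14.1, define the primary set as all randomised non-training subjects with maintenance end-tidal sevoflurane data, in the assigned arm, regardless of time in BIS range. Replaced subjects and their replacements both stay in. Align the Synopsis and 10.9.3.3.
2. Keep the time-in-range rule only for a named per-protocol sensitivity analysis, in place of the optional sentence. Reconcile its cut-off, arm, exception and scope to one version in both documents; which version is the sponsor's decision.
3. The exclusions for short maintenance, regional anesthesia and dexmedetomidine may stay if SAP 7.1.3 lists them and they apply identically in both arms. The Synopsis names a caudal block where Protocol 10.9.2 names any regional anesthesia; these must be reconciled.
4. Restate the 108 qualifying data sets (Synopsis, Protocol 14.2, SAP 6) as randomised subjects with endpoint data. Report exclusions by reason, arm and age group. Update the CIP version that the SAP cites.
5. State that data collection continues after a time-in-range exclusion. The protocol says this for the exclusions in item 3, but for time-in-range cases it promises only safety monitoring. Section 10.14 lists replacement after a deviation as a way of exiting, and 10.14.1 ends data collection at exit. Maintenance sevoflurane should already exist for these subjects; recovery data are not assured.

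**Cost:** a protocol and SAP amendment with IRB approval (Protocol 16.6), and possibly a smaller difference to detect. Because the study is powered within each age group, the 18-per-arm power figures in step 5 of the working are the relevant ones. The sponsor may need to revisit the sample size.
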